TITLE

Reduction of prostate biopsy morbidity and hospitalization through a modified biopsy protocol bundle and region-specific antibiogram.

STUDY DESIGN

Approach:

This will be a prospective multi-center cohort case-control study comparing a novel **transperineal prostate biopsy protocol** integrating measures to reduce post procedural infection (Cases) to **traditional transrectal prostate biopsies** (Controls). Eligible subjects will be identified through administrative records in the Urology clinics affiliated with Maimonides Medical Center. Eligible patients will be counseled about the risks and benefits of participation and offered enrollment into the study. Demographic data including age, comorbidities and past medical history will be extracted from the medical record.

Men meeting inclusion/exclusion criteria will be prospectively enrolled.

The novel transperineal protocol will include the following: (**Cases**)

1. Transperineal biopsy approach with avoidance of rectal flora
2. MRI-ultrasound fusion-guided biopsies with reduced number of biopsy cores, where clinically indicated
3. Rectal swab to identify the presence of fluoroquinolone resistant (FQR) bacteria
4. Multi-antibiotic prophylaxis
5. Urine culture, prostate tissue culture and rectal swab culture to define contemporary, region-specific antibiotic resistance patterns.

Traditional biopsy protocol includes: (**Controls**)

1. Transrectal approach
2. Standard 12-core template
3. Surgeon-specific antibiotic prophylaxis
4. Urine culture, prostate tissue culture and FQR rectal swab culture to define contemporary, region-specific antibiotic resistance patterns.

Inclusion criteria:

- Male patients greater than 18 years of age
- Indication for prostate biopsy

Exclusion criteria:

- Female patients
- Male patients under 18 years of age
- No indication for prostate biopsy

Statistical analysis and Sample Size Calculation:

The proposed study will consist of two treatment groups, the novel transperineal protocol and the Traditional biopsy protocol. The decision to conduct a prospective cohort case-control study compared to a randomized controlled trial was based on an assessment of feasibility.

Sample Size:

Sample size calculation was performed using the online sample size calculator at clincalc.com/stats/samplesize.aspx.

Study group design: Two independent study groups

Primary endpoint: Dichotomous (yes/no) [Any complication after biopsy]

Statistical Parameters:

Anticipated Incidence

Group 1 (Traditional/**Controls**): 18% predicted rate of any complication (Ref: Gershman et al.)

Group 2 (Transperineal bundle/**Cases**): 4% rate of any complication

Enrollment ratio: 1:1

Type I/II Error Rate:

Alpha (Type 1 error): 0.05 [5% chance of false positive]

Power (Type II error): 80% [20% chance of false negative]

[figure not shown]
Sample Size:

Group 1 (Traditional): 77

Group 2 (Transperineal protocol): 77

Total: 154

Final statistical analysis will be performed under the guidance of the available professional biostatistician.

Expected Outcomes:

Our hypothesis is that a standardized transperineal prostate biopsy protocol avoiding rectal flora and incorporating anti-microbial measures will reduce infectious complications and hospital readmissions compared to current biopsy practices. This will provide an evidence-based platform to guide Urology practices for this commonly performed procedure. We will also use culture data from the study to construct a region-specific antibiogram to determine appropriate prophylactic antibiotic coverage and tailor antibiotics for patients that develop infectious complications.

Primary Outcome Measure:

1. Rate of **any clinically significant post-biopsy complications** including infectious complications and hospital readmissions within 30 days.

Secondary Outcome Measures:

1. **Individual complications within 30 days** including urinary retention, hematuria, urinary tract infection, hospitalization.
2. Presence of antibiotic resistant bacteria. (Region-specific antibiogram)

Data Collection, Transmission and Retention:

Study data will be stored on excel sheets in a dedicated, password-protected file within the Maimonides Medical Center Information Technology network. Data will only be available to members of the study team. HIPAA rules be followed. At the conclusion of data collection, the Excel sheet will be exported to statistical analyses software with the assistance of a professional biostatistician for analysis.

Collection and storage of specimens will be performed under the supervision of the medical director of clinical laboratory services ([name]).

The following specimens will be collected and analyzed:

- i. Urine cultures
- ii. Rectal swab cultures
- iii. Prostate tissue cultures

Collection of specimens will not interfere with the appropriate clinical care pathway of study participants.

Quality of collected data will be monitored by the Principal Investigator and Co-Investigators who will work with radiologists, technicians, pathologists, and biostatisticians to ensure that information collected is accurate and reliable. Only the minimum amount of information necessary to perform the study will be collected and great care will be taken to ensure that PHI associated with the patient cases are protected, used, and destroyed according to federal and hospital policy and procedures.

The Investigator shall retain all study documentation for a period of at least (7) years or in accordance with retention policies of the GCP regulations in force or Hospital policy and IRB/EC of record, whichever is longer, following the formal discontinuation of the study.

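### Baseline risk factors for complications are not specified for standard capture or adjustment in this non-randomised comparison; a short list of fixed chart fields would be a cheap improvement

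*Combined protocol and SAP*

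**What the plan says.** - **Allocation.** Under Statistical analysis and Sample Size Calculation: "The decision to conduct a prospective cohort case-control study compared to a randomized controlled trial was based on an assessment of feasibility". No section says how a man comes to have one approach or the other.
- **Baseline data.** Study Design, Approach: "Demographic data including age, comorbidities and past medical history will be extracted from the medical record". No other covariate list or data form is given. Prostate volume, prior biopsy, anticoagulants and earlier antibiotic exposure are not named anywhere. Antibiotics appear only as prophylaxis at biopsy (in controls, "Surgeon-specific antibiotic prophylaxis") and in connection with the antibiogram and the treatment of infections.
- **Limit on data.** Data Collection, Transmission and Retention: "Only the minimum amount of information necessary to perform the study will be collected".
- **Analysis.** "Final statistical analysis will be performed under the guidance of the available professional biostatistician". No model, matching, weighting or covariate set is named.
- **Outcomes.** The primary outcome is any clinically significant complication within 30 days, with infections and readmissions given as examples. Secondary outcome 1 lists single complications, "including urinary retention, hematuria, urinary tract infection, hospitalization".
- **Planning rates.** "18% predicted rate of any complication" in controls and 4% in cases, with 77 men per group.

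**The concern.** Without randomisation, the comparison is only as good as the case that the groups carried similar risk before biopsy, or that differences were measured and removed. The listed complications have plausible pre-biopsy drivers: gland volume or earlier retention for urinary retention, anticoagulant or antiplatelet drugs for haematuria, and recent antibiotics or an earlier post-biopsy infection for infection. These links are a clinical assumption; the documents do not state them.

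The items that the plan names do not clearly reach gland volume or current and recent drugs. Free-text history may be recorded unevenly across the clinics of a multi-center study. Eligibility does not narrow the range of risk, because any adult man with an indication for biopsy qualifies. An imbalance in an unrecorded factor would be read as an effect of the bundle: it could create an apparent benefit or hide a real one.

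The missing adjustment method can still be repaired before the analysis. Fields that were not abstracted in a standard way before outcomes were known are harder to recover without bias.

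**Working it through.** **1. The plan's own figure.** Inputs from the Sample Size section: rates 0.18 and 0.04, alpha 0.05 (taken as two-sided; the plan does not say), power 80%, ratio 1:1. Mean rate = 0.11.

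n = [1.960 × √(2 × 0.11 × 0.89) + 0.842 × √(0.18 × 0.82 + 0.04 × 0.96)]² / 0.14² = 77.2 per group.

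Power at 77 per group is 79.9%. The stated 77 is reproduced.

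**2. Expected events.** 77 × 0.18 + 77 × 0.04 = 13.9 + 3.1 = about 17. At 5 to 10 events per parameter (a common rule, assumed here), an ordinary outcome regression supports about 2 to 3 parameters, including treatment.

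**3. Bias from one factor when the bundle has no effect.** All values here except the 18% are assumptions. Let g be the factor's risk ratio for any complication, a its prevalence in controls and b its prevalence in cases.

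Apparent risk ratio = [1 + b(g − 1)] / [1 + a(g − 1)]; apparent case rate = 0.18 × that ratio.

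The last column is the probability that the two-sided 5% test at 77 per group is significant in favour of the bundle: Φ[(d − 1.960 × SE₀) / SE₁], where d is the difference in rates, SE₀ the pooled and SE₁ the unpooled standard error. With no imbalance it is 2.5%.

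| Controls v cases | g | Apparent risk ratio | Case rate | False benefit |
|---|---|---|---|---|
| 40% v 30% | 1.5 | 1.15/1.20 = 0.96 | 17.3% | 3.3% |
| 40% v 30% | 3 | 1.60/1.80 = 0.89 | 16.0% | 5.2% |
| 50% v 20% | 1.5 | 1.10/1.25 = 0.88 | 15.8% | 5.4% |
| 50% v 20% | 2 | 1.20/1.50 = 0.80 | 14.4% | 8.8% |
| 50% v 20% | 3 | 1.40/2.00 = 0.70 | 12.6% | 15.1% |

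**4. The opposite direction.** Suppose the planned effect is real and the factor is commoner in cases (20% of controls v 50% of cases). Case rate = 0.04 × [1 + 0.5(g − 1)] / [1 + 0.2(g − 1)], which is 4.5%, 5.0% and 5.7% for g = 1.5, 2 and 3. Power falls from 79.9% to 75.7%, 71.9% and 65.7%.

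**5. Comparison with the planned effect.** 0.04/0.18 = 0.22. No scenario in step 3 comes near that ratio.

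**The case against.** A reader might infer that these factors will not be recorded and that the contrast cannot be corrected. The documents do not support that, for these reasons:

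- The baseline sentence gives examples, so its list is open, and the source is the chart of prospectively enrolled men. Prior biopsy, earlier infection and earlier retention can fall under past medical history. The text supports only that the items are not specified.
- The sentence about collecting the minimum is a privacy clause. Covariates needed for the comparison meet its test of necessity, so it does not exclude them.
- Retention and haematuria are named only as secondary outcomes. They enter the primary outcome only if judged clinically significant, so those two routes to bias are less direct than the infection route.
- Urine and rectal swab cultures are planned in both groups and give some patient-level data on infection risk, although their timing in controls is not stated.
- A reader might take "MRI-ultrasound fusion-guided biopsies with reduced number of biopsy cores, where clinically indicated" as evidence that the groups will differ. It qualifies fusion guidance within the case bundle and is not an allocation rule. The documents show neither the size nor the direction of any imbalance.
- A factor that drives one component needs a larger effect on that component to multiply the whole composite by 2 or 3. The upper rows of the table are therefore demanding scenarios.

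All of this stands. It limits how strongly the point can be put. It does not supply a standard record of gland volume and current or recent drugs, or a plan to use the data that are named. It is also fair to say that extra fields achieve nothing unless an adjusted comparison is specified, so the two changes belong together.

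**Conclusion.** The point holds as a cheap improvement. The comparison is non-randomised, three baseline items are named and no adjustment is specified. Standard capture of prostate volume, anticoagulant or antiplatelet use and recent antibiotic use, and correction for them, are not assured. Other relevant history may exist only in unstructured form.

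The size depends on assumed prevalences and risk ratios. With no true effect, the chance of a significant false benefit is 3.3% to 5.2% under the milder imbalance and 5.4% to 15.1% under the stronger one, against a nominal 2.5%. It would be wrong to conclude that confounding by one such factor could explain the whole planned reduction: the apparent ratio stays at 0.70 or above in every scenario shown, against 0.22 planned.

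**What to change.** Add fixed fields to the data sheet, abstracted from the chart in the same way in both groups before the outcome is known:

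- prostate volume;
- prior prostate biopsy and any earlier post-biopsy infection;
- current anticoagulant or antiplatelet use;
- antibiotic use in a fixed window before biopsy;
- catheter or earlier retention.

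Tabulate them by group. Specify in advance an adjusted comparison that uses them with age and comorbidity. With about 17 expected events they should not be entered one by one in a logistic model for the outcome. A single propensity score with weighting is one suitable choice, because the score is fitted to group membership (77 v 77) and not to the few events.

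The cost is a short addition to the data and analysis sections and modest abstraction time for 154 men. No extra patients, visits or procedures are needed. Adjustment will not remove confounding by factors that remain unrecorded.

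### Does the label FQR on the control arm's rectal culture leave the rectal antibiogram with 77 men instead of 154?

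*Combined protocol and SAP*

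**What the plan says.** The rectal test appears in three places in the combined protocol and SAP.

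- **STUDY DESIGN, Cases, items 3 and 5.** Item 3 is "Rectal swab to identify the presence of fluoroquinolone resistant (FQR) bacteria". Item 5 is "Urine culture, prostate tissue culture and rectal swab culture to define contemporary, region-specific antibiotic resistance patterns".
- **STUDY DESIGN, Controls, item 4.** There is one entry: "Urine culture, prostate tissue culture and FQR rectal swab culture to define contemporary, region-specific antibiotic resistance patterns".
- **Data Collection, Transmission and Retention.** The specimen list has "Rectal swab cultures", next to urine and prostate tissue cultures, and names no arm.

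The antibiogram is in the title and is the second secondary outcome. Expected Outcomes describes its use: "We will also use culture data from the study to construct a region-specific antibiogram to determine appropriate prophylactic antibiotic coverage". No section gives the culture medium, the panel of drugs tested, or the antibiogram's denominator.

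**The concern.** Case item 5 and control item 4 are the same sentence except for the inserted FQR. In case item 3 the protocol attaches that term to a presence test, which it lists apart from the culture. A reader could therefore take the control test to be the item 3 screen under another name. Controls would then supply fluoroquinolone-resistance status but no profile for other drugs, and the rectal part of the antibiogram for those drugs would come from the transperineal arm alone.

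The antibiogram is meant to inform the choice of prophylaxis, so resistance to other drugs matters. Statistical help for the analysis is also described at a late stage: "At the conclusion of data collection, the Excel sheet will be exported to statistical analyses software". If the arms were processed differently, it might be noticed only then.

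**Working it through.** **Where 77 and 154 come from.** They are the sample size for the primary endpoint, not an antibiogram target. Inputs from the Sample Size section: 18% and 4% with any complication, alpha 0.05 (taken as two-sided), 80% power, 1:1 enrolment. With the pooled-variance formula and mean rate 0.11:

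n = [1.96 × √(2 × 0.11 × 0.89) + 0.842 × √(0.18 × 0.82 + 0.04 × 0.96)]² / 0.14² ≈ 77.2 per group.

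The plan's 77 per group and 154 in total are reproduced to within rounding; power at 77 per group is 79.9%. None of these inputs involves a culture result.

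**The wordings side by side.**

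| Feature | Cases, item 3 | Cases, item 5 | Controls, item 4 | Specimen list |
|---|---|---|---|---|
| Called a culture | no | yes | yes | yes |
| FQR named | yes | no | yes | no |
| Purpose | detect FQR bacteria | define resistance patterns | define resistance patterns | none given |

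Control item 4 agrees with case item 5 on two features (culture, purpose) and with case item 3 on one (the FQR label). The specimen-list entry is generic and fits either arm, so it is not a third version. The discrepancy is one qualifier, cases against controls.

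**What each reading implies.**

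| Component | Same culture in both arms | Control culture selective for FQR |
|---|---|---|
| Rectal FQR carriage, per man | up to 154 | up to 154 |
| Urine cultures | both arms | both arms |
| Prostate tissue cultures | both arms | both arms |
| Rectal resistance to other drugs, unselected men | up to 154 | up to 77 |

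Only the last row differs. These are ceilings, because missing specimens are not allowed for.

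**Size of that one difference.** The documents give no resistance rates, so the rates below are assumptions. The 95% half-width is 1.96 × √[p(1 − p)/n].

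| Assumed p | n = 154 | n = 77 |
|---|---|---|
| 10% | 4.7 points | 6.7 points |
| 20% | 6.3 points | 8.9 points |
| 30% | 7.2 points | 10.2 points |

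At 20%: 1.96 × √(0.16/154) = 0.063 and 1.96 × √(0.16/77) = 0.089. The ratio is √(154/77) = 1.41 at every rate. The plan sets no precision target against which 8.9 points could be called inadequate. The half-widths count men; a table built on isolates would have a different n, which the documents do not allow one to work out.

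**The case for a change.** The best argument for acting is that the ambiguity is real and cheap to remove. No section says outright that the control culture is unselective. If it were selective, control isolates would come only from FQR carriers: about 8 to 23 of 77 men at an assumed carriage of 10% to 30% (0.10 × 77 = 7.7; 0.30 × 77 = 23.1). Pooling those with unselected case isolates could overstate resistance, which would be worse than a wider interval.

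Part of this stands. The wording does differ, and isolates selected for resistance should not be pooled with unselected ones. The rest carries less weight:

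- The selective reading sits badly with control item 4 itself, since a screen for one resistance would largely fail its stated purpose of defining resistance patterns.
- Pooling of isolates is not planned. The size of any bias depends on isolates per swab and on the denominator, neither of which is stated.
- That control-arm data would be lost for good is not shown. Specimens are to be collected and stored under the clinical laboratory's medical director, and nothing says that swabs or isolates are discarded. That role, not the biostatistician's, bears on the culture method.
- Rewording the list would add no data. If control swabs really were only screened, tidier text would leave the same 77 men in the table.

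**Conclusion.** The concern does not hold as a reason to change the plan. The inconsistency is a single qualifier between case item 5 and control item 4. The shared purpose, the word culture in the control entry, and a specimen list common to the study all favour the same rectal culture in both arms. On that reading nothing is lost or biased.

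On the less supported reading, the effect is limited to rectal resistance to drugs other than fluoroquinolones: at most 77 men instead of 154, with intervals 1.41 times as wide (8.9 against 6.3 points at an assumed 20%). FQR carriage, urine and tissue results cover both arms either way. The primary endpoint and the 77 per group do not depend on any culture.

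What remains is a detail that the people doing the work fill in. The laboratory knows which medium and panel it uses, and an analyst tabulating an antibiogram gives the number tested for each specimen type and keeps differently processed specimens apart. No number or rule in the plan is shown to be wrong. This conclusion rests on reading the text as a whole, because the documents do not describe the laboratory method.
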